## **Pre-existing Conditions**

In this study, a pre-existing condition is a disorder/disease present before the AE-reporting period starts (i.e., prior to the subject signing the ICF) and noted on the Medical History eCRF. A pre-existing condition should not be reported as an AE unless the condition worsens or episodes increase in frequency during the AE-reporting period.

## 7.2 Adverse Events Associated with Study Procedures

## **Visual Acuity**

A worsening of BCVA of 3 lines or more in logMAR score should be captured in the source documents and the appropriate AE eCRF.

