**Table 1: Schedule of Assessments** 

	Screening/ Randomization Phase	Dosing Phase (16 Days)				Evaluation Phase (15 Days)		
Evaluation 	Visit 1 Day -14 to Day -2	Phone Call Day -3 (±1)	Visit 2 Day 0 (Day of Surgery)	Visit 3 Day 1 (+1)	Visit 4 Day 8 (±1)	Visit 5 Day 15 (+1)	Visit 6 Day 18 (-1/+2)	Visit 7 Day 29 (± 2)
Written Informed Consent	X							
Demographics	X							
Entry Criteria	X							
Medical/Medication History	X							
Urine Pregnancy Test	X							X
Slit Lamp Biomicroscopy 	X			X	X	X	X	X
Visual Analog Scale	X			X	X	X	X	X
Intraocular Pressure	X			X	X	X	X	X
Best Corrected Visual Acuity	X			$X^3$	X	X	X	X
Ophthalmoscopy 	X					X	X 	X 
Confirm and Document Subject Eligibility	X							
Randomization	X							
Dispense IP and Pain/Dosing Diary	X							
Instruct Subject on IP and Dosing/Pain Diary	X							
AE Assessment	X	X	X	X	X	X	X	X
Dosing Reminder Call		X						
Update Concomitant Medications			X	X	X	X	X	X
Review Pain/Dosing Diary			X	X	X	X	$X^4$	X 
Collect IP						X	X 	X 
Collect Pain/Dosing Diary							X	X 
Exit Subject From Study			_					X

IP = Investigational Product; AE = adverse event; eCRF = electronic case report form

<sup>1All eye exams are to be conducted in the study eye only. The fellow eye (non-study eye) may be examined at the investigators' discretion.

<sup>2Performed by a board-certified ophthalmologist.

<sup>3A pinhole test may be employed at Day 1 (Visit 3).

<sup>4Dosing terminates on Day 14. Pain is assessed through the evening of Day 17.

<sup>5If not completed at previous visit.

Note: Unscheduled visits may occur during the study period. All assessments will be recorded on the eCRF for unscheduled visits, but it is up to the investigator which assessments to conduct. If the subject exits early, all Visit 7 assessments should be conducted, including ophthalmoscopy if not obtained at Day 15 (Visit 5).

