#### **6.2** Examination Procedures

The following ophthalmic examinations will be conducted in the surgery eye (study eye) at intervals specified in Table 1, The Schedule of Assessments. The fellow eye (non-study eye) may be examined at the investigators' discretion.

- **Best Corrected Visual Acuity (BCVA):** BCVA will be measured at every visit except Visit 2 (Surgery; Day 0). The Early Treatment Diabetic Retinopathy (ETDRS) log of the minimum angle of resolution (logMAR) will be used to measure BCVA.
- Intraocular Pressure (IOP): IOP will be measured at every visit except Visit 2 (Surgery; Day 0) in mmHg using an applanation tonometer.
- **Ophthalmoscopy**: Ophthalmoscopy will be performed at Visit 1 (Day -14 to Day -2) and Visit 5 (Day 15) by a board-certified ophthalmologist.
- **Biomicroscopy:** Slit lamp biomicroscopy, including the evaluation of ACC and anterior chamber flare (ACF), chemosis, bulbar conjunctival injection, ciliary injection, corneal edema, and keratic precipitates will be conducted by a board-certified ophthalmologist at every visit except Visit 2 (Surgery; Day 0).
- Visual Analog Scale (VAS): Eye pain/discomfort and photophobia will be evaluated at every visit except Visit 2 (Surgery; Day 0) using a Visual Analog Scale (VAS), scoring from 0 to 100 using a mark on a 100 mm line (0 = absent; 100 = maximum).
- Pain assessment via diary (Pain Diary): Surgery eye pain will be evaluated prior to each IP dose using a pain scale included in the pain and dosing diary that subjects complete at home.

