## **IOP**

An increase in IOP of  $\geq$  10 mmHg from Visit 1 or any subsequent visit should be captured as an AE in the source documents and on the AE eCRF.

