## **Biomicroscopy**

Anterior chamber cell (ACC) and ACF, chemosis, bulbar conjunctival injection, ciliary injection, corneal edema, and keratic precipitates will be assessed in the study. Since the severity of these assessments will be recorded and carefully monitored during the study, worsenings do not need to be recorded as AEs unless the investigator judges it appropriate. Any treatment emergent findings (findings that were not present prior to dosing with IP, or a worsening relative to baseline [before IP dosing]) outside of these assessments should be recorded as an AE.

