# **Ophthalmoscopy**

A new finding or a significant worsening (2 units or more) from baseline should be recorded as an AE.

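### Does the 3-line visual acuity trigger for adverse events need a stated reference point?

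*Protocol*

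**What the plan says.** The visual acuity rule in Protocol 7.2 is one sentence: "A worsening of BCVA of 3 lines or more in logMAR score should be captured in the source documents" and on the AE form. It sets a size, 3 lines, and no comparator. No other section supplies one for this trigger.

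The neighbouring mandatory triggers in 7.2 do have one:

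- **IOP:** a rise of 10 mmHg or more "from Visit 1 or any subsequent visit should be captured as an AE".
- **Slit-lamp findings outside the listed signs:** new, or worse than the state before dosing.
- **Ophthalmoscopy:** "A new finding or a significant worsening (2 units or more) from baseline should be recorded as an AE".

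VAS pain and photophobia and the listed slit-lamp signs have no mandatory trigger; recording them is left to the investigator.

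Section 6.2 and Table 1 have BCVA measured at Visit 1 and on Days 1, 8, 15, 18 and 29, with a pinhole test allowed on Day 1 (Table 1, footnote 3). Section 8.3 lists BCVA, measured and as change from baseline at each scheduled visit, among the safety endpoints.

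**The concern.** Visit 1 is the only BCVA reading before dosing, and it is taken in an eye awaiting cataract removal. The BCVA entry limit in 3.1 applies to the fellow eye only, so the study eye may start with poor acuity and improve after surgery. A site that compares with Visit 1 alone could then see a clear post-operative decline that is still no worse than the starting value, and the trigger would stay silent. A site that compares with the previous visit would record the same course as an AE.

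Ocular safety is a stated objective and the incidence of ocular AEs is a safety endpoint. If sites read the sentence differently, the count of BCVA events would depend partly on the site. An analysis plan cannot make AE recording uniform after the fact. The optional Day 1 pinhole reading adds a smaller uncertainty: the rule does not say whether it may serve as a comparator.

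**Working it through.** The protocol states no figure on this point, so there is nothing to reproduce. Two checks apply: the line arithmetic under a Visit 1 reading, and the cost of the obvious rewording.

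**1. What a Visit 1 reading would miss**

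Inputs: trigger of 3 lines (7.2); 1 line = 0.1 logMAR (assumption), so 0.3 logMAR; gain of g lines from Visit 1 to the post-operative best (not in the protocol, assumed 0 to 6). Higher logMAR is worse.

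A loss of L lines from the post-operative best leaves the eye L − g lines worse than at Visit 1. The trigger fires when L − g ≥ 3, that is, L ≥ g + 3.

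| g (assumed) | Fires at a loss of | Losses of 3 lines or more not flagged |
|---|---|---|
| 0 | 3 | none |
| 1 | 4 | 3 |
| 4 | 7 | 3 to 6 |
| 6 | 9 | 3 to 8 |

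Example with assumed values: Visit 1 at 0.6, Day 8 at 0.0, Day 15 at 0.4 logMAR. Day 15 is (0.4 − 0.0)/0.1 = 4 lines worse than Day 8, yet (0.6 − 0.4)/0.1 = 2 lines better than Visit 1.

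**2. What still captures such a loss**

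- Section 7.0 requires new or worsening conditions after consent to be recorded as AEs, has subjects asked a standard question about problems, and tells them to report unusual ocular events between visits.
- Section 7.1 defines an AE to include any unfavourable sign or symptom, and makes sight-threatening AEs serious.
- The six scheduled BCVA readings are collected, so a loss between any two visits can be derived from the data whatever the AE form says.

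**3. What an any-earlier-visit rule would add**

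Simulated subjects have constant true acuity and independent normal errors. A subject is flagged if any later post-surgical reading is at least 0.3 logMAR (3 lines) worse than any earlier one. Four readings (Days 8, 15, 18, 29) give 4 × 3/2 = 6 pairs; adding Day 1 gives 5 × 4/2 = 10. Whole-line scoring rounds each reading to a line, with a random starting offset. Expected flags among 240 subjects:

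| Assumed SD (logMAR) | Continuous, 6 pairs | Continuous, 10 pairs | Whole lines, 6 pairs | Whole lines, 10 pairs |
|---|---|---|---|---|
| 0.05 | 0.02 | 0.03 | about 0.6 | about 1 |
| 0.06 | 0.28 | 0.46 | about 3 | about 5 |
| 0.08 | 5.1 | 8.0 | about 18 | about 28 |
| 0.10 | 19.7 | 29.7 | about 43 | about 62 |

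For instance, at SD 0.10 with continuous scores and 6 pairs, 8.21% × 240 = 19.7. If Visit 1 also counts as a reference and g = 0, Visit 1 plus Days 8 to 29 already makes five readings, so the 10-pair columns apply even without Day 1.

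**The case for a change.** The best case for a change is that it costs one sentence and no new measurement. The IOP rule just below already shows the wording, and the recording instruction has to be right before data are collected. Every other mandatory trigger in 7.2 names its reference, so the omission looks like an oversight. The neighbouring rules also follow two conventions (baseline, or Visit 1 and any later visit), so a site borrowing from them could go either way, and the baseline convention is the one that can miss a loss.

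Much of this stands. The omission is real, the line arithmetic is correct, and an analysis plan cannot standardise AE entries afterwards.

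It does not stand that a site has nothing to go on. The slit-lamp and ophthalmoscopy rules and the BCVA endpoint in 8.3 all point to baseline, which the schedule makes Visit 1. The bare word for worsening equally allows comparison with any earlier visit. Divergence between sites is possible but not shown. Nor is a loss that fails the numeric trigger thereby unrecorded. The rewording is not a clear gain either: at the larger assumed SDs it would add noise events that could outnumber the real ones it is meant to catch.

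**Conclusion.** No change follows. This is a definition left unwritten, not a wrong rule: nothing in the protocol contradicts the visual acuity sentence, and it can be applied sensibly as it stands.

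The possible harm is confined to one numeric prompt. Under a Visit 1 reading it misses losses of 3 to g + 2 lines, where g is unknown; how often that course would occur cannot be computed from the protocol. General AE recording and the per-visit BCVA data remain as safeguards. Surgery is common to both arms and the trial is randomised and masked, so differences in how sites read the rule do not bias the comparison of BCVA between arms.

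Choosing a reference is a trade-off. Baseline alone gives few noise flags but can be blind after a surgical gain. Any earlier visit catches every 3-line decline, but with assumed SDs of 0.05 to 0.10 logMAR it flags about 0 to 30 of 240 stable subjects with continuous scores, or about 1 to 62 with whole-line scores. Those flags would be expected in the 2:1 allocation ratio. The range rests on independent normal errors and constant true acuity; the SDs are not from the protocol. The pinhole question matters only if Day 1 is used as a comparator, and is minor.

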## **IOP**

An increase in IOP of  $\geq$  10 mmHg from Visit 1 or any subsequent visit should be captured as an AE in the source documents and on the AE eCRF.

## **Biomicroscopy**

Anterior chamber cell (ACC) and ACF, chemosis, bulbar conjunctival injection, ciliary injection, corneal edema, and keratic precipitates will be assessed in the study. Since the severity of these assessments will be recorded and carefully monitored during the study, worsenings do not need to be recorded as AEs unless the investigator judges it appropriate. Any treatment emergent findings (findings that were not present prior to dosing with IP, or a worsening relative to baseline [before IP dosing]) outside of these assessments should be recorded as an AE.

# **Ophthalmoscopy**

A new finding or a significant worsening (2 units or more) from baseline should be recorded as an AE.

#### VAS

Pain/discomfort and photophobia will be assessed in the study eye. Since the severity of these assessments will be recorded and carefully monitored during the study, worsenings do not need to be recorded as AEs unless the investigator judges it appropriate.

## 7.3 Reporting and Evaluation of AEs and SAEs

Table 2 presents the reporting guidelines for AEs and SAEs. It is important that the investigator comply with the SAE reporting timelines in order to assure that safety reporting timelines of IRB/IEC and regulatory authorities such as the FDA can be met.

**Table 2:** Requirements for Reporting Adverse Events and Serious Adverse Events to Sponsor

Туре	Reporting Time	Type of Report
Serious	Within 24 hours	Adverse Event Report (AE eCRF) Serious Adverse Event Report Form
Non-serious	Per eCRF submission procedure	Adverse Event Report (AE eCRF)

All information relevant to the SAE must be recorded on the appropriate SAE Report Form, and the form submitted immediately (within 24 hours of learning of the event) to the sponsor Medical Monitor or designee:

The investigator must also provide sponsor or designee a copy of all pertinent medical records such as source documents, hospitalization records, death certificates etc. that are de-identified and contain only the study subject number and the subject initials. The investigator should maintain a copy of these medical records in his/her files, as well as any information and medical judgments from colleagues or other medical personnel who assisted in the treatment and follow-up of the subject.

The investigator should ensure that the subject receives appropriate medical treatment and follow-up. Subjects should receive follow-up until the SAE resolves or resolves with sequelae (as judged by the investigator).

## **Institutional Review Board or Independent Ethics Committee**

The investigator will inform the IRB/IEC of any SAE/serious, unexpected, suspected adverse reaction according to the IRB/IEC's specific reporting guidelines.

For all serious, unexpected, suspected adverse reactions, the sponsor or designee will provide documentation to the investigator for the investigator's report to the IRB/IEC or local regulatory authorities.

The investigator must provide documentation of all such IRB/IEC notifications to the sponsor or designee. Copies of each report must be kept in the investigator's files.

## 7.4 Follow-up of Adverse Events and Serious Adverse Events

All AEs, regardless of severity, will be followed throughout the study to the final study visit, until they resolve or resolve with sequelae (as judged by the investigator).

At the final study visit, new AEs, as well as follow-up information for continuing AEs, will be recorded in the eCRF and source document. Non-serious ongoing AEs will be followed beyond the final study visit at the discretion of the investigator and recorded in the source documents.

If an SAE is unresolved at the final study visit, it will be followed by the investigator until it resolves or resolves with sequelae (as judged by the investigator). Follow-up data for such SAEs will be recorded in the source document and reported to the sponsor or designee.

Subjects withdrawn from the study due to an AE or SAE will be followed by the investigator until the outcome is determined (resolved or resolved with sequelae) and, where appropriate, additional written reports and documentation will be provided to the sponsor.

### 8.0 STATISTICAL ASSESSMENTS

## 8.1 Primary Efficacy Endpoint

The primary efficacy endpoint is the proportion of subjects with an ACC grade of 0 at Day 15.

Anterior Chamber Cells				
Grade*	Cell Count			
0	0			
1	1-5			
1	6-10			
2	11-20			
3	21-50			
4	> 50			

\*Grade 1 includes cell count 1-5 and cell count 6-10.

## 8.2 Secondary Efficacy Endpoint

The secondary efficacy endpoints are the proportion of subjects who achieve a pain score of 0 on the visual analog scale (VAS) (0-100 mm scale) for each post-surgical assessment at Days 1, 8, 15, 18, and 29.

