#### 2.0 STUDY DESIGN

This study is a Phase 3, randomized, multicenter, double-masked, vehicle-controlled, parallel-group clinical trial. Approximately 240 subjects will participate in the study and will be randomized in a 2:1 ratio to the ISV-305 group (160 subjects) and the vehicle group (80 subjects).

Written informed consent will be obtained from all subjects prior to any study-specific procedure. Subjects will be enrolled into a 16-day dosing phase, followed by a 2-week evaluation phase. There will be 7 visits scheduled during the study: a screening visit between 2 and 14 days prior to surgery; 3 visits during the dosing phase (Day 0 [Surgery Day], Day 1, and Day 8); and 3 visits during the evaluation phase (Day 15, Day 18, and Day 29). In addition, there will be a telephone call on Day -3 to remind subjects to begin dosing on Day -1, the day before surgery. Subjects will instill 3 doses prior to surgery (2 doses on Day -1, and 1 dose on Day 0 prior to surgery), 1 dose in the evening after surgery and continue dosing BID for 14 days after surgery.

Subjects will be randomized and receive instructions for dosing at home and completing a pain and dosing diary. Subjects will be cautioned to dose only for the specified amount of time. One bottle of investigational product (IP) will be dispensed to the subject, and a second bottle will remain at the site as a precaution only in the event of loss, etc., and will not be dispensed unless necessary. Throughout this protocol, the surgery eye is referred to as the study eye, and the fellow eye is referred to as the non-study eye.

All ratings and procedures should be performed by the same examiner from visit to visit whenever possible. Additional exams may be scheduled as necessary to ensure the safety of the subjects during the study period.

Subjects who terminate use of IP for any reason will be withdrawn from the study, the reason(s) clearly described on the subject's electronic Case Report Form (eCRF) and source documents, and the sponsor or designee will be notified.

If the investigator determines lack of efficacy during the dosing period, administration of a rescue medication (i.e., another medication to treat ocular inflammation and/or ocular pain in the surgery eye [study eye]) must occur after subject is withdrawn from the study, and be clearly documented on the source documents and the designated eCRF.

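### Does rescue medication given after Day 14 turn failures into pain-free successes at Days 18 and 29?

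*Protocol*

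**What the plan says.** Three parts of the protocol bear on this.

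- **Rescue rule (section 2.0).** The trigger is worded for one phase: "If the investigator determines lack of efficacy during the dosing period, administration of a rescue medication" is to follow withdrawal, in that it "must occur after subject is withdrawn from the study". A second withdrawal trigger is early stopping of study drug: "Subjects who terminate use of IP for any reason will be withdrawn from the study".
- **Timing (Table 1, footnote 4, and section 2.0).** "Dosing terminates on Day 14. Pain is assessed through the evening of Day 17". Section 2.0 schedules "3 visits during the evaluation phase (Day 15, Day 18, and Day 29", so three of the five post-surgical pain assessments come after the last planned dose.
- **Endpoint (section 8.2).** The measure is the "proportion of subjects who achieve a pain score of 0 on the visual analog scale (VAS", taken "for each post-surgical assessment at Days 1, 8, 15, 18, and 29". Rescue is not mentioned.

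Two further provisions matter. Inclusion criterion d (section 3.1) requires subjects to be willing to stay off disallowed medication for the whole study, not just while dosing. Table 1 has concomitant medications updated at Visits 2 to 7, that is, through Day 29.

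**The concern.** Read side by side, sections 2.0 and 8.2 seem to treat one event in two ways. A subject rescued on Day 10 has to leave the study first. A subject rescued on Day 16 falls under no stated rule, can attend Days 18 and 29, and meets the endpoint as worded if the VAS mark is at 0.

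In a vehicle-controlled trial of an anti-inflammatory drug, one would expect more late rescue on vehicle. If so, and if rescue were ignored in the scoring, the comparison at those two visits would become study drug against vehicle plus rescue. The observed difference would shrink, and two of the five secondary time points would say less about the drug itself.

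**Working it through.** **Step 1. What the text fixes.** The link between rescue and withdrawal is limited to the dosing period (section 2.0), dosing ends on Day 14 (Table 1), and section 8.2 has no rescue qualifier. These observations are correct. The concern needs two more statements, and neither is in the protocol:

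- *That a late-rescued subject counts as a success.* Section 8.2 gives the variable, the scale and the days. Section 8 lists endpoints only. It has no analysis sets, missing-data rule, test or rule for rescue, so silence there cannot be read as an instruction to ignore rescue.
- *That an early-rescued subject drops out of the data.* Section 2.0 takes the subject out of the study. It does not say the subject leaves the analysis, and the note to Table 1 asks for all Visit 7 assessments at early exit. Such a subject could be analysed as a non-responder.

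Without these two statements, no inconsistency in scoring before and after Day 14 has been shown.

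**Step 2. Whether the data would support a rule.** Concomitant medications are updated at each visit from Day 0 to Day 29, so use of another anti-inflammatory or pain medication after Day 14 can be identified. An SAP could count such subjects as failures, or not, without any change to data collection.

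**Step 3. The possible size.** The protocol gives no response rate, rescue rate, alpha or power, so there is no planned figure to reproduce beyond the allocation: 240 × 2/3 = 160 and 240 × 1/3 = 80, as stated. All rates below are assumptions.

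Let p be the pain-free rate without rescue, r the share rescued after dosing, and q the share of those who score 0. If rescue is ignored:

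- rate in an arm = p + q·r
- difference = (p_active − p_vehicle) − q·(r_vehicle − r_active)

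The loss is q·(r_vehicle − r_active), which is zero when late rescue is equal in the two arms.

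Power uses the two-proportion normal approximation with a pooled null variance, two-sided 0.05, n = 160/80: power = Φ[(difference − 1.96·SE0)/SE1]. SE0 uses the pooled rate and SE1 the separate rates.

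With p = 75% v 50% and q = 70%:

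| Late rescue, active v vehicle | Rates if rescue is ignored | Difference (points) | Power |
|---|---|---|---|
| none | 75.0% v 50.0% | 25.0 | 97% |
| 5% v 5% | 78.5% v 53.5% | 25.0 | 98% |
| 2% v 5% | 76.4% v 53.5% | 22.9 | 95% |
| 5% v 10% | 78.5% v 57.0% | 21.5 | 93% |
| 5% v 20% | 78.5% v 64.0% | 14.5 | 67% |
| 10% v 30% | 82.0% v 71.0% | 11.0 | 50% |

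For the 5% v 20% row: 75 + 0.7 × 5 = 78.5; 50 + 0.7 × 20 = 64.0; loss 0.7 × 15 = 10.5 points.

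A second set, p = 80% v 60% with every rescued subject scoring 0 (q = 100%), starts at 20 points and 90.1% power:

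- 2% v 5% rescued: 17 points, 81.9%
- 3% v 10%: 13 points, 63.3%
- 5% v 15%: 10 points, 47.3%
- 5% v 5%: 20 points, 93.1%

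The large losses come only from the rows with strongly unequal rescue. High late rescue on vehicle is also doubtful: subjects judged to lack efficacy while dosing leave before rescue, so those who reach Day 15 are a selected group. The tables keep the full 160/80 and make no allowance for those departures.

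**The case for a change.** The strongest reply is that this is more than an SAP matter. The protocol itself sets the endpoint definition and ends the rescue rule at Day 14. It also asks for rescue to be documented on a designated eCRF only within that rule, and an SAP cannot recover data that were never collected. Criterion d is an entry condition and does not say how to count a subject who is treated later. The expected direction, more rescue on vehicle, is reasonable if the drug works.

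Part of this stands. The protocol is silent on rescue in the evaluation phase, criterion d does not fill that gap, and unequal late rescue would shrink the difference if rescue were ignored. Day 15 also follows the last planned dose, so the silence is not confined to Days 18 and 29.

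The data argument does not stand, because concomitant medications are recorded through Day 29. Nor does the claim that the plan has chosen wrongly. Scoring pain regardless of rescue (a treatment-policy estimand) and scoring rescue as failure (a composite estimand) are both defensible for secondary assessments made after treatment has ended. The protocol commits to neither.

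**Conclusion.** The concern does not hold. The rescue rule is worded for the dosing period and section 8.2 does not mention rescue, but nothing in the protocol makes a late-rescued subject a success or removes an early-rescued one from the analysis. How rescue enters a responder analysis is commonly settled in the SAP, which is not available here, and the visit schedule already collects what such a rule would need.

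The size cannot be fixed from the protocol. In the first set of assumptions it runs from no loss (equal late rescue) to 14 points (10% v 30% rescued, difference 25.0 down to 11.0). Any loss requires more late rescue on vehicle and a scoring rule that ignores it, and neither is stated. The primary endpoint, anterior chamber cell grade 0 at Day 15, is not part of this concern.
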